I agree to make available to Sponsor personnel, their representatives, and relevant regulatory authorities, my patients' study records in order to verify the data that I have entered into the Case Report Forms. I am aware of my responsibilities as a Principal Investigator as provided by the Sponsor.

I understand that the Sponsor may decide to suspend or prematurely terminate the study at any time for whatever reason; such a decision will be communicated to me in writing. Conversely, should I decide to withdraw from execution of the study, I will communicate my intention immediately in writing to the Sponsor.

Print Name

Signature

Principal Investigator

Title

Date (DD MMM YYYY)

PROTOCOL SYNOPSIS

| | |
|---------------------------------|--|
| EudraCT: | 2015-005732-18 |
| IND Numbers: | IND 77,254 for Stroke, IND 63,266 for Deep Vein Thrombosis/Venous Thromboembolism |
| Protocol Number: | DU176b-A-U157 |
| Investigational Product: | Edoxaban (free base of edoxaban tosylate) |
| Active Ingredient(s)/INN: | Edoxaban tosylate: N -(5-Chloropyridin-2-yl)- N' -[(1 S ,2 R ,4 S)-4-(N,N -dimethylcarbamoyl)-2-(5-methyl-4,5,6,7-tetrahydro[1,3]thiazolo[5,4- c]pyridine-2-carboxamido)cyclohexyl] oxamide mono (4-methylbenzenesulfonate) monohydrate |
| Study Title: | A Phase 1, Open-label, Single-dose, Non-randomized Study to Evaluate Pharmacokinetics and Pharmacodynamics of Edoxaban in Pediatric Patients |
| Study Phase: | Phase 1 |
| Indication Under Investigation: | Not applicable. |
| Study Objectives: | 
Primary:
 
• To characterize the PK of edoxaban in pediatric patients following single-dose oral administration 
Secondary:
 
• To evaluate the PD effects of edoxaban in pediatric patients following single-dose oral administration• To evaluate the safety and tolerability of single-dose oral administration of edoxaban in pediatric patients• To assess metabolite exposure (D21-2393, D21-3231, D21-1402, and D21-2135) in pediatric patients• To evaluate the palatability (bitterness, sweetness, and overall taste or aroma) of the liquid oral suspension of edoxaban |

Study Design:

This is a Phase 1, open-label, multiple-center study in pediatric patients from 38 weeks gestation to < 18 years of age. Patients from 5 age cohorts (12 evaluable patients per age cohort) will receive a single dose of edoxaban. Each age cohort will be divided into a low- and high-dose group (6 patients per dose group). Order of enrollment will be from the oldest age cohort to the youngest age cohort. Within each age cohort, enrollment will first start in the lower dose group (to achieve exposures comparable to a 30 mg adult dose). After evaluation of PK and safety data from at least half the patients in the lower dose group, enrollment may then start in the higher dose group (to achieve exposures comparable to a 60 mg adult dose). If the observed exposures are higher than expected in the lower dose group and exceed the projected 60 mg adult exposure, then a lower dose may be investigated in the proposed “high-dose” group. Enrollment in the next younger age cohorts will begin when at least 50% of patients have completed the study in the older age cohort. Enrollment in the younger age cohorts will start only after PK and safety data have been evaluated from at least 6 patients (3 low-dose and 3 high-dose) in the older age cohort. Pharmacokinetic and safety data will be reviewed by a Data and Safety Monitoring Board (see Section 11.9) who will approve the start of the next younger age cohort. However, enrollment initiation of Cohort 5 may be considered without PK and safety data from at least 50% of patients in the preceding older dose group.

Age cohorts and dose groups:

- 12 to < 18 years of age on the day of dosing (12 evaluable total patients)
 - Cohort 1a: Low-dose group (6 patients)
 - Cohort 1b: High-dose group (6 patients)
 - 6 to < 12 years of age on the day of dosing (12 evaluable total patients)
 - Cohort 2a: Low-dose group (6 patients)
 - Cohort 2b: High-dose group (6 patients)
-

-
- 2 to < 6 years of age on the day of dosing (12 evaluable total patients)
 - Cohort 3a: Low-dose group (6 patients)
 - Cohort 3b: High-dose group (6 patients)
 - 6 months to < 2 years of age on the day of dosing (12 evaluable total patients)
 - Cohort 4a: Low-dose group (6 patients)
 - Cohort 4b: High-dose group (6 patients)
 - 38 weeks gestation to < 6 months of age on the day of dosing (12 evaluable total patients)
 - Cohort 5a: Low-dose group (6 patients)
 - Cohort 5b: High-dose group (6 patients)

In Cohort 1, the oldest age group (12 to < 18 years), doses have been selected on the basis of modeling of adult data to target comparable exposures to 30 mg (low-dose) and 60 mg (high-dose). In this cohort, fixed dosing will be used. In Cohorts 2, 3, 4, and 5, the younger age groups (38 weeks gestation to < 12 years), appropriated doses will be selected to elicit target exposures comparable to those achieved from adult doses of 30 mg (low-dose) or 60 mg (high-dose). Patients in Cohort 1 will receive multiples of edoxaban tablets of 30 mg strength. Patients in Cohorts 2, 3, 4, and 5 will receive the edoxaban granule for oral suspension. The dose that each dose group receives will be determined by Daiichi Sankyo based on emerging PK data and modeled doses needed to achieve target exposures.

For patients in Cohort 1, 7 serial blood samples (2 mL per sample) will be collected for PK analysis based on a sampling windows approach: 0.25 to 1 hour, 1.5 to 3 hours, 3.5 to 6 hours, 6.5 to 8 hours, 8.5 to 14 hours, 24 to 36 hours, and 48 to 54 hours postdose. Additionally, 6 serial PD blood samples (1.8 mL per sample) will be collected for estimation of biomarkers of coagulation (prothrombin time [PT], activated partial thromboplastin time [aPTT], and anti-activated factor X [FXa]) at predose and immediately after simultaneously scheduled PK blood samples at 0.25 to 1 hour, 1.5 to 3 hours, 3.5 to 6 hours, 6.5 to 8 hours, and 24 to 36 hours postdose.

For patients in Cohorts 2 and 3, 5 serial blood samples (patients 6 to < 12 years of age: 2 mL per sample and

patients < 6 years of age: 1 mL per sample) will be collected for PK analysis based on a sampling windows approach: 0.25 to 1 hour, 1.5 to 3 hours, 4 to 8 hours, 9 to 14 hours, and 24 to 36 hours postdose. Additionally, 6 serial PD blood samples (patients 6 to < 12 years of age: 1.8 mL per sample and patients < 6 years of age: 1 mL per sample) will be collected for estimation of biomarkers of coagulation (PT, aPTT, and anti-FXa) at predose and immediately after simultaneously scheduled PK blood samples at 0.25 to 1 hour, 1.5 to 3 hours, 4 to 8 hours, 9 to 14 hours, and 24 to 36 hours postdose.

For patients in Cohort 4, 4 serial blood samples (600 μ L per sample) will be collected for PK analysis based on a sampling windows approach: 0.5 to 2 hours, 3 to 8 hours, 9 to 14 hours, and 24 to 36 hours postdose. Additionally, 2 PD blood samples (1 mL per sample) will be collected for estimation of biomarkers of coagulation (PT, aPTT, and anti-FXa): once at the Screening Visit and once immediately after simultaneously scheduled PK blood sample at 0.5 to 2 hours postdose.

For patients in Cohort 5, blood samples (600 μ L per sample) will be collected for PK analysis at a total of 3 of the 4 possible timepoints postdose: 0.5 to 2 hours (mandatory), 3 to 8 hours, 9 to 14 hours, and 24 to 36 hours. The timepoints will be assigned by the Sponsor once the subject is approved to be randomized. The Investigator will be informed of the PK timepoints to be collected for Cohort 5. Additionally, 2 PD blood samples (1 mL per sample) will be collected for estimation of biomarkers of coagulation (PT, aPTT, and anti-FXa): once at the Screening Visit and once immediately after simultaneously scheduled PK blood sample at 0.5 to 2 hours postdose.

Although windows for sample collection are allowed, the exact time and date of each blood sample will be recorded in the patient's Case Report Form.

| | |
|-------------------------------|--|
| Study Duration: | 
The study will last approximately 4 weeks for each patient, which will include a screening period (within 21 days of dosing), a treatment period, and a follow-up visit conducted within 10 days after dosing. However, a patient will be considered to have completed the study if they provide the last scheduled PK sample. The treatment period will consist of predose procedures occurring on Day -1 or 1, dosing on Day 1, and postdose procedures occurring postdose on Days 1, 2 (all cohorts) and Day 3 (all patients enrolled prior to Version 5.0 of the protocol may have had Day 3 PK samples obtained). The treatment period days may occur as in-patient or out-patient based on the clinic's ability/discretion. The overnight stays are not mandatory. Check-out procedures will be performed after the last PK/PD blood samples are collected (Day 2 or Day 3).
 
The first patient is expected to be enrolled in June 2014.
 |
| Study Sites and Location: | Multiple sites in North America, Europe, and other regions |
| Planned Sample Size: | A total of 60 patients will be enrolled to obtain 12 evaluable patients in each age cohort (6 patients in each dose group). |
| Patient Eligibility Criteria: | 
Male and female pediatric patients who may require or are currently on anticoagulant therapy may be enrolled.
 
These may include:
 
• Patients who have a recently acquired or Investigator determined ongoing risk of thromboembolic events (e.g., patients with thrombophilia, congenital heart disease, presence of a central venous catheter and prior venous thromboembolic event [VTE]).• Patients who are completing their standard-of-care anticoagulant therapy. Edoxaban can be initiated 12 hours after cessation of enoxaparin, dabigatran, or apixaban therapy (A-U136, A-U151, and A-E152) and 24 hours after cessation of rivaroxaban therapy (A-U151). Note: that the dose of edoxaban should be at the time of the next scheduled standard-of-care anticoagulant administration:
– At least 4 hours after last dose of unfractionated heparin. |

- At least 12 hours after last dose of twice daily (bid) low molecular weight heparin (LMWH).
 - At least 24 hours after last dose of once daily (qd) LMWH and synthetic pentasaccharide (SP) Xa inhibitors.
 - For patients who were on a prior vitamin K antagonist (e.g., warfarin [C-U122] and any other anticoagulants) therapy, international normalization ratio (INR) value should be ≤ 2.5 prior to edoxaban dosing. If the patient's INR is > 2.5 , the patient's INR should be monitored until it is ≤ 2.5 .
- Patients who are currently treated for VTE with at least 5 days of heparin may interrupt their standard-of-care anticoagulant therapy for edoxaban administration. The dose of edoxaban should be:
 - At least 12 hours from last dose of bid LMWH, with a restart of LMWH 24 hours after edoxaban dose.
 - At least 24 hours from last dose of qd LMWH, with a restart of LMWH 24 hours after edoxaban dose.
- Patients with cardiac conditions who may require anticoagulant therapy.
- Patients with sickle cell disease who may require anticoagulant therapy.

For any condition, anticoagulant treatment interruption or discontinuation should not take place if the patient is at increased risk and should be appropriate as per standard-of-care practices.

Dosage Form, Dose, and Route of Administration:

Edoxaban tablets (30 mg) or edoxaban granules for oral suspension (60 mg reconstituted with 8 mL water to provide a 6 mg/mL suspension for oral administration). In each age cohort, patients will receive appropriated single oral dose selected to target exposures comparable to adult doses of 30 mg (low-dose) or 60 mg (high-dose). If the observed exposure from the 30 mg dose in adolescents is higher than predicted and is comparable to the 60 mg adult dose exposures, then, the next cohort will receive a lower dose, instead of a higher dose. To allow for this flexibility, patients in the 12 to < 18 years of age cohort will receive edoxaban tablets of 30 mg strength. Patients younger than 12 years of age will receive the edoxaban granule for oral suspension. The dose amount given to each patient will be determined based on emerging data. The dose given may be updated based on emerging data.

The PK model will be refined based on emerging data, modeling of a target age and weight range will establish dosing paradigms. The PK modeling will account for the range of weights.

If a patient is unable or unwilling to ingest the assigned dosing form (tablet or suspension formulation), the patient will not be enrolled and will be replaced.

Patients will be administered edoxaban in the morning with water.

- Cohorts 1a/1b: 120 mL water;
- Cohorts 2a/2b: 60 mL water;
- Cohorts 3a/3b: 40 mL water;
- Cohorts 4a/4b: 10 mL water;
- Cohorts 5a/5b: 10 mL water.

Patients will be asked to fast for at least 4 hours before dosing and for an additional 2 hours after dosing. If this is not feasible because of the patient's age or other needs, (unflavored) milk, or an equivalent substitute liquid (but not fruit juices), will be allowed until 1 hour before and starting at 1 hour postdose. During this period, the total volume of liquids should not exceed 240 mL, excluding the volume of water utilized for dosing.

Study Endpoints:

Pharmacokinetics:

The PK endpoints will include modeled PK parameters such as apparent systemic clearance (CL/F), apparent volume of distribution (V/F), and area under the concentration-time curve (AUC) for edoxaban and metabolites, and metabolite/parent ratios for AUC.

Pharmacodynamics:

The PD endpoints will include observed, change-from-baseline, and percent-change-from-baseline PT, aPTT, and anti-FXa.

Safety:

Safety assessments will include: adverse events (AEs), physical examination findings, vital signs, standard hematology, clinical chemistry, and urinalysis laboratory tests. Note: urinalysis will be performed with plastic bags with a sticky strip from neonates and infants with diapers.

Other:

Palatability of the liquid formulation will be assessed using visual analog scale (VAS) scores.

Pharmacokinetics/

Pharmacodynamics/

Statistical Analyses:

Plasma concentration-time data for edoxaban and metabolites (if data are available) will be listed by patient, age cohort and/or dose group, and measurement time interval, and will be plotted and summarized using descriptive statistics, as appropriate. Plasma concentration-time data for edoxaban and metabolites will be analyzed using model-based approaches such as nonlinear mixed effects modeling, where data from other studies may be pooled with pediatric data, and PK parameters will be calculated. Estimated PK parameters will be assessed for age dependencies using graphical and/or modeling methods. Estimated PK parameters will be listed and summarized by age cohort and/or dose group using descriptive statistics.

An exploratory analysis of variance model will be applied to natural log-transformed CL/F, V/F, and AUC with age cohort, dose, and age cohort by dose interaction as fixed factors. Appropriate adjustments on parameters, e.g., dose-normalization on AUC, or body weight-normalization on CL/F and V/F, might also be explored. The least-squares mean differences between age cohorts with age cohort of 12 to < 18 years as the reference and the corresponding 95%

confidence intervals (CIs) will be exponentiated to obtain point estimates of ratios of geometric means and the corresponding 95% CIs by dose level and/or overall (as appropriate).

For PD biomarkers (PT, aPTT, and anti-FXa), observed, change-from-baseline, and percent-change-from-baseline data will be listed by patient, age cohort and/or dose group, and measurement time interval, and will be plotted and summarized using descriptive statistics, as appropriate.

The PK/PD relationships will be examined graphically to assess age dependencies. Additional PK/PD modeling may be conducted, if necessary, to understand age dependencies.

The VAS scores for palatability will be listed and summarized by age cohort and/or dose group using descriptive statistics, if data permit.

TABLE OF CONTENTS

| | |
|---|----|
| INVESTIGATOR AGREEMENT..... | 2 |

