4.1.1. Inclusion Criteria

Male and female pediatric patients who may require or are currently on anticoagulant therapy may be enrolled.

These may include:

- Patients who have a recently acquired or Investigator determined ongoing risk of thromboembolic events (e.g., patients with thrombophilia, congenital heart disease, presence of a central venous catheter and prior VTE).
- Patients who are completing their standard-of-care anticoagulant therapy. Edoxaban can be initiated 12 hours after cessation of enoxaparin, dabigatran, or apixaban therapy (A-U136, A-U151, and A-E152) and 24 hours after cessation of rivaroxaban therapy (A-U151). Note: that the dose of edoxaban should be at the time of the next scheduled standard-of-care anticoagulant administration:
 - At least 4 hours after last dose of unfractionated heparin.
 - At least 12 hours after last dose of bid LMWH.
 - At least 24 hours after last dose of qd LMWH and SP Xa inhibitors.
 - For patients who were on a prior vitamin K antagonist (e.g., warfarin [C-U122] and any other anticoagulants) therapy, INR value should be ≤ 2.5 prior to edoxaban dosing. If the patient's INR is > 2.5 , the patient's INR should be monitored until it is ≤ 2.5 .

- Patients who are currently treated for VTE with at least 5 days of heparin may interrupt their standard-of-care anticoagulant therapy for edoxaban administration. The dose of edoxaban should be:
 - At least 12 hours from last dose of bid LMWH, with a restart of LMWH 24 hours after edoxaban dose.
 - At least 24 hours from last dose of qd LMWH, with a restart of LMWH 24 hours after edoxaban dose.
- Patients with cardiac conditions who may require anticoagulant therapy.
- Patients with sickle cell disease who may require anticoagulant therapy.

For any condition, anticoagulant treatment interruption or discontinuation should not take place if the patient is at increased risk and should be appropriate as per standard-of-care practices.

Patients must satisfy all of the following criteria to be included in the study. Any temporal changes in the following criteria that may prohibit patient consideration, but should normalize for future eligibility, should be reassessed for the patient's future participation in the study:

1. Patients/legal guardian(s) must be able to provide written informed assent (patient, when applicable) and ICFs (signed by parent/legal guardian) prior to participating in the study.

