4.1.2. Exclusion Criteria

Patients who meet any of the following criteria will be disqualified from entering the study. Any temporal changes in the following criteria that may prohibit patient consideration, but should normalize for future eligibility, should be reassessed for the patient's future participation in the study:

1. Patients with abnormal coagulation tests during screening, as defined by local laboratory reference ranges, which are not explained by anticoagulant therapy or temporary concomitant affections.
2. Patients with stroke where anticoagulant therapy is contraindicated.
3. Patients with stage 2 hypertension defined as blood pressure confirmed $> 99^{\text{th}}$ percentile + 5 mmHg.
4. Patients with renal function less than 50% of normal for age and size as determined by the National Kidney Disease Education Program version of the Schwartz formula (see Appendix 17.5).⁸
5. Actively bleeding, has a high risk of bleeding, or has a history of major bleeding.
6. Has a currently active gastrointestinal ulceration or a known history of peptic ulcer or gastrointestinal bleeding (including hematemesis, melena, or rectal bleeding including bleeding from hemorrhoids) within the previous 3 months.
7. Has known diabetic retinopathy.
8. Has thrombocytopenia at screening ($< 20 \times 10^9/\text{L}$).
9. Patients with history of major trauma, major or invasive procedures within the last month prior to screening. Otherwise, shorter time may be permitted depending on the surgery and based on the Investigator's judgment of bleeding risk.
10. Patients with known malabsorption disorders (e.g., cystic fibrosis or short bowel syndrome). Otherwise, shorter time may be permitted depending on the surgery and based on the Investigator's judgment.

11. Hepatic disease which is associated with coagulopathy leading to a clinically relevant bleeding risk, alanine transaminase (ALT) > 5 times the upper limit of normal (ULN), or total bilirubin > 2 times the ULN with direct bilirubin > 20% of the total.
12. Patient is currently enrolled in another investigational device or drug study or is receiving other investigational agents. Patients must have completed the prior clinical study at least 30 days prior to dosing.
13. Patients of childbearing potential (post-menarche) who are sexually active and are not using approved contraception, per local practice; who are pregnant (as based on test results); or are breastfeeding.

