6.1. Screening

Screening will take place within a 3-week window (Days -21 to -2) before dosing. Informed consent will be obtained from the patient/guardian prior to performing any of the screening assessments. For information regarding re-screening, see Section [4.2.4](#).

The following activities and/or assessments will be performed at/during screening:

- Informed consent (for parent/legal guardian/patient) and depending on the age of the patient, an assent form may also be signed by the patient.
- Inclusion/exclusion criteria.
- Record demographic information (date of birth/age, sex, ethnicity, and race).
- Medical and surgical history, including medication history.
- AE monitoring.
- Concomitant medication monitoring.
- Physical examination, including height, weight, and BMI (derived).
- Pregnancy test based on local practice (for post-menarchal females).
- Patients of childbearing potential (post-menarche) who are sexually active must agree to use an effective contraception method, per local practice, for the duration of the study.
- Blood samples for:
 - Clinical laboratory tests (hematology and serum chemistry) if not performed within 2 weeks prior to screening (refer to Section [9.6](#)).
 - Coagulation (PT, INR, and aPTT).
 - Serology (human immunodeficiency virus [HIV] and hepatitis B and C testing) if not performed within 2 weeks prior to screening.
 - PD blood samples for Cohorts 4 and 5.

- Urine sample for:
 - Urine drug screen for the presence of the following controlled substances: opiates, benzodiazepines, amphetamines, cannabinoids, cocaine, barbiturates, phencyclidine, cotinine levels (non-exclusionary), and alcohol will be performed on patients 12 years of age and older, for newborns, and for patients who are being breastfed.
 - Urine sample for dipstick analysis. Microscopic analysis may be required if dipstick is positive for blood, RBC, or WBC.
- Vital signs including blood pressure, pulse rate, and body temperature after resting at least 5 minutes in a sitting or supine position. (Note: the appropriate cuff size based on arm circumference will be used).

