Exact dates and times of dosing and sample collection will be recorded in the patients' CRFs and used for analyses. At time points when PK, and PD blood samplings occur at the same time, the PK blood samples will be collected first and then PD blood samples will be collected. An overnight stay on Day 1 is not mandatory.

6.3.3.2. Day 2

On Day 2, the following procedures will be performed:

- **All Cohorts:**

- AE monitoring.
- Concomitant medication monitoring.

- **Cohort 1, 2, and 3:**

- PK blood samples will be collected using a window approach at 24 to 36 hours postdose.
- PD blood samples for estimation of biomarkers of coagulation (aPTT, PT, and anti-FXa) immediately after collection of the simultaneously scheduled PK samples at 24 to 36 hours postdose.

- **Cohort 4:**

- PK blood samples will be collected using a window approach at 24 to 36 hours postdose.

- **Cohort 5:**

- Note: For this cohort, only 3 of 4 possible PK timepoints will provide a blood specimen. For patients who provided only 2 PK blood samples on Day 1, a 3rd PK

blood sample will be collected at 24 to 36 hours. No PK blood samples will be collected for patients who provided 3 PK blood samples on Day 1.

Note: the overnight stay on Day 1 is not required; however, the above procedures will occur on Day 2. Some patients may be given the option to have a home healthcare service conduct the Day 2 procedures in the patient's home, depending on the availability of the service in the patient's country. Exact dates and times of dosing and sample collection will be recorded in the patients' CRFs and used for analyses. At time points when PK and PD blood samplings occur at the same time, the PK blood samples will be collected first and then PD blood samples will be collected.

6.3.3.3. Day 3

On Day 3, the following procedures will be performed:

- **PK blood samples for Cohort 1:** will be collected using a window approach at 48 to 54 hours postdose.
- Vital signs (including blood pressure, pulse rate, and body temperature) will be taken 48 to 54 hours postdose. All vital sign assessments will be performed before the scheduled blood sampling for edoxaban and after at least a 5-minute rest in a sitting or supine position. The position in which the vital signs are taken (i.e., sitting or supine) will be recorded in the CRF.
- AE monitoring.
- Concomitant medication monitoring.

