1. The overnight stay on Day 1 or Day 2 is not mandatory. The patient may leave the clinic on Day 1 following the completion of all study procedures and return to the clinic on Day 2 for the completion of Day 2 procedures (or Day 3 for patients enrolled prior to Version 5.0 of the protocol). Any procedure occurring after hour 8 on Day 1 may be performed using a home healthcare service, depending on the availability of the service in the patient's country.
2. Check-in may occur on Day -1 or 1, depending on the site.
3. Some patients may be given the option to have a home healthcare service conduct the procedures for this visit in the patient's home, depending on the availability of the service in the patient's country.
4. Blood samples will be obtained at screening if not drawn within 2 weeks prior to screening.
5. Serum chemistry will only be obtained from patients in Cohorts 1, 2, and 3.
6. Only 1 assessment required prior to edoxaban dosing at either screening or upon check-in, as appropriate for the patient.
7. Doses will be selected based on emerging PK and safety data.
8. Patients receiving the edoxaban granule for oral suspension formulation who are developmentally capable of providing an accurate response will be asked to rate several aspects of palatability (including bitterness, sweetness, overall taste, and aroma) using 100 mm VAS. Patients who are old enough will score the VAS themselves. For younger children, the parents will provide this information, if possible. For the youngest children, there will be free text input available to provide information on whether the patient spit it out and may not have liked the flavor, etc.
9. Continuous monitoring after screening procedures are complete.
10. Refer to cohort-specific PK/PD SOE for specific timepoints.

Table 17.2: Pharmacokinetic and Pharmacodynamic Blood Sampling Schedule for Cohort 1

| Study Day → | Days -21 to -2 | Day -1/1 predose | | Day 1 ¹ | | | | | Day 2 ¹ | Day 3 ¹ | Within 10 days after dosing |
|------------------------------------|----------------|-----------------------|---------|----------------------|----------------------|----------------------|----------------------|-----------------------|-----------------------------------|----------------------|-----------------------------|

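### Three limited gaps in the secondary PD summaries: LMWH restart not ordered against the 24-36 h draw (Cohorts 1-3), percent change in anti-FXa undefined at a zero baseline, and a screening-only baseline (Cohorts 4-5)

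*Combined protocol and SAP*

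**What the plan says.** **Late draw, Cohorts 1-3.** Section 4.1.1 lets patients under treatment for VTE interrupt LMWH for the edoxaban dose, "with a restart of LMWH 24 hours after edoxaban dose". Section 6.3.3.2 (Day 2) takes the last PD sample "immediately after collection of the simultaneously scheduled PK samples at 24 to 36 hours postdose". Neither section, nor Section 5.2 on concomitant medication, says which comes first.

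**Scales.** The synopsis and Sections 3.1.3 and 11.5.2 name observed value, change from baseline and percent change for PT, aPTT and anti-FXa alike. Note 1 to Table 1.1 records that, in the sponsor's ex vivo study, no change in anti-FXa could be computed because the baseline was 0.

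**Baseline, Cohorts 4-5.** The two PD draws are taken "once at the Screening Visit and once immediately after simultaneously scheduled PK blood sample at 0.5 to 2 hours postdose" (Synopsis, Study Design). Section 6.1 lists "PD blood samples for Cohorts 4 and 5" among the screening bloods, and screening runs from Day -21 to Day -2. Table 17.1 marks a predose PD draw for all cohorts, but its footnote 10 says "Refer to cohort-specific PK/PD SOE for specific timepoints", and Table 17.4 has no predose PD draw. Exclusion criterion 1 (Section 4.1.2) removes only abnormal coagulation tests "which are not explained by anticoagulant therapy or temporary concomitant affections", so a screening value raised by an anticoagulant does not bar entry.

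**Analysis rules.** Section 11.1.2 leaves patients out of the PD set for clinically significant events or protocol deviations that compromise the PD results. Section 11.2 brings all evaluable data into the analyses and refers to a separate SAP for full detail. Section 11 does not define the PD baseline and has no rule for a sample taken under another anticoagulant.

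**The concern.** PT, aPTT and anti-FXa respond to other anticoagulants as well as to edoxaban. The protocol recognises this for heparin: Section 6 bars heparin flushes, and Section 17.2.2 warns of heparin contamination of PD samples. It gives no matching analysis rule for therapeutic heparin. Followed as written, the 24-36 h summary in Cohorts 1-3 can report LMWH effect as edoxaban effect. A change value in Cohorts 4-5 can report the withdrawal, or the presence, of another drug. One named endpoint can be incalculable for some patients.

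PD is a secondary objective, and Section 11.5.2 uses PK/PD plots to look for age dependence. The baseline itself changes with age: predose in Cohorts 1-3, screening in Cohorts 4-5. With 6 patients per dose group, one affected patient is 1/6 = 17% of a summary.

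**Working it through.** The documents give no PD sample size, power or effect figure, so there is no stated figure to reproduce. Section 11.10 covers CL/F and V/F only.

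**1. Late draw against LMWH restart (Cohorts 1-3).**
- Ceiling: 3 × 12 = 36 of 60 patients, and among these only patients treated for VTE who interrupt LMWH. The documents do not say how many that is.
- Draws: Section 8.2.1 gives 1 predose and 5 post-dose PD samples, so 1 of 5 (20%) is at 24-36 h. The samples up to 14 h come before any restart.
- Order: the restart is at 24 h and the window is 36 − 24 = 12 h long, opening at the restart hour. With an on-time restart, only a draw right at 24 h could come first.
- Edoxaban left by then, using adult 60 mg steady-state values (Section 1.1.1.5) as a guide only: 15.5/303 = 5.1% of peak at 24 h. With the stated half-life of 10 to 14 h, the 36 h level is 15.5 × 2^(−12/10) = 6.7 to 15.5 × 2^(−12/14) = 8.6 ng/mL, or 2.2% to 2.8% of peak. The interval holds little edoxaban information, so LMWH could dominate a reading.
- Filter: a restart that follows the protocol is not a deviation, so Section 11.1.2 does not clearly remove the value.

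**2. Percent change in anti-FXa.** Percent change = 100 × (rise)/(baseline). The values here are assumed: a rise of 1.0 in all six patients of a dose group, five of them with baseline 0.5 (100 × 1.0/0.5 = 200% each).

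| Sixth baseline | Sixth patient | Group mean | SD | Median | Mean absolute change |
|---|---|---|---|---|---|
| 0.2 | 500% | 250% | 122 | 200% | 1.0 |
| 0.1 | 1,000% | 333% | 327 | 200% | 1.0 |
| 0.05 | 2,000% | 500% | 735 | 200% | 1.0 |
| 0 | undefined | n falls to 5 | | | 1.0 |

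For example, (5 × 200 + 2,000)/6 = 500%. Absolute change is unaffected throughout.

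**3. Screening baseline (Cohorts 4-5).**
- Ceiling: 2 × 12 = 24 of 60 patients. Each has one post-dose PD sample, so the patient's only change value rests on the screening sample.
- Let e be the true edoxaban effect and b the factor by which an agent gone by dosing had raised the screening value; both are assumed. Computed change = (1 + e)/b − 1. With e = 50%, b = 1.25, 1.5 and 2.0 give +20%, 0% and −25%. One such patient of six with b = 2.0 moves a group mean of 50% to (5 × 50 − 25)/6 = 37.5%.
- The opposite error is also possible. If the agent was absent at screening but still raises the post-dose value 1.25-fold, the computed change is 1.5 × 1.25 − 1 = +87.5%.
- Observed post-dose values do not use this baseline at all.

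**The case against.** The strongest reply is that much of this rests on silence. Section 11.2 sends full detail to a separate SAP that is not in the text reviewed. The definition of baseline, sample flags and non-calculable values are ordinary SAP content, and Section 11.5.2 calls for summaries only where appropriate. This stands as a limit on confidence. Confirming that such rules exist would settle much of the point.

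The late draw is one of five, in few patients, at an interval with little edoxaban. Medications are recorded (Section 5.2), and for samples "Exact dates and times of dosing and sample collection will be recorded", so affected values can be found afterwards. That makes the effect small, but it also makes a prespecified rule cheap. On percent change, the plan already reports n, median and range, so an extreme value would be visible; the endpoint is still undefined at zero. The two-draw schedule in Cohorts 4-5 sits beside strict blood limits (1% at any time, 3% in 4 weeks), and analysis cannot create a better baseline. That also stands.

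Some stronger readings are not supported:
- A reader might infer that the restart and draw passages contradict each other. Both can be followed; only their order is missing.
- Table 17.1 might suggest a predose draw in Cohorts 4-5, but its footnote defers to the table that has none.
- The differing baselines might suggest a bias in a known direction with age. Predose baselines in Cohorts 1-3 can also carry residual drug, since dosing is allowed "At least 12 hours after last dose of bid LMWH", so no direction follows.
- Section 4.2.4 rechecks INR after warfarin, and Table 17.1 footnote 6 allows the safety PT, INR and aPTT at check-in. Some later values may therefore exist, but neither covers anti-FXa or is named as the PD baseline.

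**Conclusion.** The point holds as three limited problems in secondary summaries that Section 11.2 treats as descriptive and exploratory. A change is worth making because it is cheap. The late draw can reflect LMWH in at most 36 of 60 patients. The change values in Cohorts 4-5 can be biased either way in at most 24 of 60. Percent change in anti-FXa is incalculable at a zero baseline, and its mean is unstable near zero. These are ceilings: the number of patients on another anticoagulant is not stated, patients on none are unaffected, and the effect sizes shown rest on assumed values.

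A reader might infer that dose finding or the PK conclusions are compromised. They are not: dose prediction uses PK concentrations (Section 11.8), and the primary objective and Section 11.10 concern PK. Confidence is medium, because the separate SAP and the CRF were not available.

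**What to change.** 1. **Restarted anticoagulant.** In Section 11.5.2 and the SAP, exclude from PD summaries and PK/PD plots any PT, aPTT or anti-FXa value drawn after another anticoagulant was restarted. List it with a flag and keep the paired PK concentration. Confirm that the CRF captures the restart time. The sponsor should state how the 24-36 h draw and the 24 h restart are ordered; no timing is proposed here.
2. **Anti-FXa scale.** Report observed value and absolute change only, and align the synopsis, Section 3.1.3 and Section 11.5.2. Percent change stays for PT and aPTT.
3. **Cohorts 4-5 baseline.** Prespecify a programmable flag: any recorded start, stop or interruption of an anticoagulant between the screening PD sample and the edoxaban dose. Make observed post-dose values the main display. Show change from baseline for all patients and again without flagged patients, noting that the second version may rest on anywhere from 0 to 6 patients per dose group. This exposes the problem but does not repair the baseline.

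**Cost.** No added blood, no moved draw and no change to the PK windows. A few 24-36 h PD values leave the summaries, and there is one more descriptive table. The endpoint wording, and any text ordering the restart and the draw, need protocol edits, which go through the review described in Section 15.1.
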